6.4 STUDY INTERVENTION COMPLIANCE

Full compliance with the intervention is defined as completing all 5 daily stimulation sessions for 40 minutes each day. As the intervention is applied and monitored by research personnel, compliance can be directly observed.

6.5 CONCOMITANT THERAPY

Eligible subjects will be permitted to be receiving concomitant therapy, such as psychotherapy, antidepressants, or other medications. The only medications not permitted during this trial are anticonvulsants and recent benzodiazepines. The use of antidepressants or other therapies may affect our outcome, as subjects may experience relief of their depressive symptoms from these treatments. However, eligibility for this trial includes stable medication for the past 4 weeks. An adequate dose of antidepressants includes at least 4 weeks of use, so we anticipate that this requirement will reduce the potential bias for permitting the use of antidepressants and other medications. We also aim to ensure a stable dosing of antidepressant medication during the study.

To ensure that concomitant therapies are logged appropriately, subjects will be requested to report any changes to the researchers. Furthermore, concomitant therapies (pharmacotherapy, psychotherapy) will be logged at Screening, D1, D5 and follow-up visit. Subjects will be requested to include the dosing for these therapies (i.e., how often per day, how much in each pill, how many pills) as well as when they were first prescribed the medication.

6.5.1 RESCUE MEDICINE

N/A

7. STUDY INTERVENTION DISCONTINUATION AND PARTICIPANT DISCONTINUATION/WITHDRAWAL

7.1 DISCONTINUATION OF STUDY INTERVENTION

Discontinuation from the week of stimulation does not mean discontinuation from the study, and remaining study procedures should be completed as indicated by the study protocol. If a clinically significant finding is identified (including, but not limited to changes from baseline) after enrollment, the investigator or qualified designee will determine if any change in subject management is needed.

The study intervention (i.e., the 5 consecutive days of stimulation) will be discontinued for the following reasons:

- A subject develops significantly increased suicidal risk, as determined by an acute assessment by [name] or [name].
- A subject has a YMRS score greater than or equal to 12.

- The subject misses a single day of stimulation and is unable to make it up at the end of the stimulation week.
- The subject fails to complete the online suicidality questions within 72 hours of receiving the survey email and a personal phone contact does not explain the omission.
- Any clinical adverse event (AE), laboratory abnormality, intercurrent illness or other medical condition, or situation occurs such that continued participation in the study would not be in the best interest of the subject.
- The subject meets any exclusion criteria (either newly developed or not previously recognized).

If the subject withdraws from the intervention, the subject will be contacted and invited for the 2-week follow-up assessment including all respective questionnaires. This assessment is not intended as a clinical follow-up with the participants but serves research purpose only.

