8.2.2 DEVELOPMENT OF MANIA

The Young Mania Rating Scale (YMRS) [28] was designed to assess the severity of manic symptoms at enrolment, with the ability to track changes over the duration of participation. When undergoing treatment for depression, a possible side effect (as inferred from clinical trials with antidepressant medications) is to alter levels of serotonin, potentially associated with mania [29], [30]. Although we do not expect such an event to occur since we are not using a medication that targets serotonin levels, we will be conducting this assessment at Day 1, Day 5 and during the 2-week follow-up as a precautionary measure. If a participant develops any sign of mania (YMRS > 12), [name] will conduct an acute assessment to determine if they are experiencing mania. If this occurs during the week of stimulation, participation in the study will be stopped and their primary mental health care provider or family physician will be contacted. In the case that they do not see anyone for their depression, [name] will assist in creating a medical care plan

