9.4.4 SAFETY ANALYSES

As discussed in **Section 8.2, Safety and Other Assessments** safety will be assessed with the three questions from the daily suicide questionnaire, the C-SSRS, an adverse effects questionnaire, and the Young Mania Rating Scale (YMRS).

The suicide questionnaire is used as a screening to assess increase in suicidal ideation (SI) or suicidal behavior (SB) daily. The C-SSRS will be used to assess suicide risk more thoroughly. If a participant's responses on either tool indicate SI or SB, the subject will be contacted, and an acute assessment will be completed if deemed necessary by [name] or [name] (as described above). Any verified increases in suicidal ideation will be described in counts/percentages and compared between groups using chi-square tests.

The stimulation questionnaire will be administered following every stimulation session, for a total of 5 administrations per participant. This questionnaire solicits ratings of 14 possible adverse effects associated with electrical stimulation, on a scale of 1 (absent) to 4 (severe). Paired t-tests with random effect "subject" will be calculated per adverse effect to determine if there are any differences in adverse effect severity between groups (sham/placebo, 10 Hz tACS). Severity per adverse effect will be described with mean and standard deviation.

The Young Mania Rating Scale (YMRS) will be used to assess any development of mania over the course of treatment. A YMRS score of greater than 12 indicates the possible development of a manic episode. Any subject who scores greater than 12 on the YMRS will be assessed by [name] or [name]. Any verified manic episode will be described in counts/percentages and compared between groups using a chi-square test.

The Adverse Events Structured Interview will be administered by research personnel following every stimulation session and at the follow up visit, for a total of 6 time points per participant. This interview solicits open-ended descriptions of 11 possible adverse effects a participant may experience in any clinical trial as well as one question of 'any other experiences'. Responses will be reviewed by the clinician and rated as described in **Section 8.3**. Paired t-tests will be calculated per adverse effect to determine if there are any differences in adverse effect severity between groups (sham/placebo, 10 Hz tACS). Severity per adverse effect will be described with mean and standard deviation.3.

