10.1.6 SAFETY OVERSIGHT

Safety oversight will be under the direction of the Principal Investigator [name]. He will review all adverse events timely and serious adverse events and changes in the suicidality and mania ratings immediately. Based on his review, continuation of participant's participation is decided. All SAE or unanticipated AE will be reported to the local IRB.

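### A YMRS score of exactly 12 ends stimulation under section 7.1 but does not require the acute mania assessment in 8.2.2 and 9.4.4 (minor)

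*Combined protocol and SAP*

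**What the plan says.** **Mania threshold.** Section 7.1 (Discontinuation of Study Intervention) includes this stopping reason: "A subject has a YMRS score greater than or equal to 12". Section 8.2.2 (Development of Mania) sets its condition as "If a participant develops any sign of mania (YMRS > 12" and, when that is met, says a named clinician "will conduct an acute assessment to determine if they are experiencing mania". Section 9.4.4 (Safety Analyses) repeats the stricter cut-off, once for what the score indicates and once for the action: "Any subject who scores greater than 12 on the YMRS will be assessed by" a named clinician. It then states the analysis: "Any verified manic episode will be described in counts/percentages and compared between groups using a chi-square test".

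**General safeguards.** For a clinically significant finding after enrollment, 7.1 says "the investigator or qualified designee will determine if any change in subject management is needed". Section 10.1.6 (Safety Oversight) has the principal investigator review "changes in the suicidality and mania ratings immediately", and lets that review decide whether the participant continues. Neither rule carries a YMRS threshold.

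**What stopping means.** Section 7.1 separates stopping stimulation from leaving the study and invites the participant to the 2-week follow-up. For suicidality, 7.1 stops stimulation when an acute assessment finds significantly increased risk. Section 8.2.1 has clinicians decide whether an acute assessment is needed and, after it, whether participation ends; hospitalization ends it automatically. Section 2.3.1 instead says that a participant whose suicide risk increases will be asked to leave the study. Section 8.2.2 says that, during the stimulation week, it is study participation that stops.

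**The concern.** A stopping rule and the examination that explains it should start at the same score. Here the protocol is sure enough at 12 to end treatment, yet requires nobody to find out whether the participant is manic until the score reaches 13. Staff who follow the sections literally would discontinue stimulation and have no instruction to arrange the mania assessment. What is at stake is a required clinical check at the score where the protocol already treats the participant as a safety case.

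The second matter is smaller. If staff apply 2.3.1, or one reading of 8.2.2, a participant stopped for suicide risk or mania leaves the study. If they apply 7.1, the same participant is invited back at 2 weeks. The choice affects follow-up and safety data for exactly the participants in whom those data matter most.

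**Working it through.** No figure in the plan needs reproducing, so the check sets the rules side by side. It assumes whole-number YMRS totals.

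| YMRS total | 7.1: stop stimulation (12 or above) | 8.2.2: acute assessment (above 12) | 9.4.4: clinician assessment (above 12) |
|---|---|---|---|
| 11 or below | No | No | No |
| 12 | **Yes** | **No** | **No** |
| 13 or above | Yes | Yes | Yes |

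The sections disagree at one value, 12.

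**When the disagreement can arise.** On timing, 8.2.2 says "we will be conducting this assessment at Day 1, Day 5 and during the 2-week follow-up as a precautionary measure". At the follow-up visit no stimulation remains to be stopped, so the 7.1 threshold has no work to do and the sections do not collide. The conflict is confined to scores obtained on Day 1 or Day 5.

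**Whether another rule supplies the assessment at 12.** The 7.1 clause on clinically significant findings leaves management to the investigator's judgment. Section 10.1.6 requires prompt review and a decision on continuation. Either could lead to an assessment, and neither says that one must be done.

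**Disposition wording.**

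- *Suicide risk.* 7.1 and 8.2.1 fit together: clinicians decide on an acute assessment, significantly increased risk ends stimulation, follow-up is offered, and participation ends only by clinician decision or hospitalization. 2.3.1 differs in both trigger (any increase) and consequence (leaving the study).
- *Mania.* 8.2.2 is ambiguous in two ways. The event that stops participation could be a score above 12 or confirmed mania. Participation may also be used loosely for stimulation, as 7.1 itself does in one of its reasons for stopping the intervention.

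**What the disposition wording can change.** Section 8.3.4 records non-serious adverse events to 7 days, and serious ones to 30 days, after the last day of participation. Take a participant stopped on Day 5, with the follow-up visit at its nominal Day 22:

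- Participation ends on Day 5: windows close on Day 5 + 7 = Day 12 and Day 5 + 30 = Day 35.
- Participation runs to Day 22: windows close on Day 22 + 7 = Day 29 and Day 22 + 30 = Day 52.

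The difference is 17 days for each window. The serious-event window passes Day 22 either way, so the main exposure is later non-serious events and the follow-up visit itself.

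**The case against.** The best defence is that a score of 12 is not ignored. Stimulation stops, the principal investigator sees the mania rating at once and decides on continuation, and 7.1 lets the investigator change management. A deliberate two-tier rule, with a cautious stop and a higher bar for assessment, is also conceivable. The safeguards are real and keep the point minor. They leave the assessment to discretion, however, and nothing in the protocol describes a two-tier rule.

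A reader might infer that a manic episode at a score of 12 would go uncounted in the safety analysis. The documents do not support that. Section 9.4.4 counts any verified episode and does not restrict the count by score. Adverse-event interviews after every stimulation day and at follow-up, reviewed by a clinician, can also bring an episode to light.

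A reader might also infer that care is withheld. It is not: referral and care planning are handled separately in 2.3.1, 8.2.1 and 8.2.2, and 7.1 says the follow-up visit after withdrawal is for research only.

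On disposition, section 7 is the dedicated discontinuation section and would probably prevail over one sentence in a risk summary. That is fair, and it is why this part is offered as a wording correction only.

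**Conclusion.** The threshold rule is wrong as written, and the fault is minor. At a YMRS of exactly 12 the protocol ends stimulation without requiring the check for mania that it requires at 13. The general rules in 7.1 and 10.1.6 reduce the gap but do not close it. This rests on the current text of 7.1, 8.2.2, 9.4.4 and 10.1.6 and on whole-number scoring. The documents give no frequency for such scores, so the number of participants affected cannot be estimated.

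The wording point is secondary. Section 2.3.1 is clearly out of line with 7.1 and 8.2.1; 8.2.2 is ambiguous rather than contradictory. No effect on the primary EEG analysis is claimed.

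**What to change.** 1. In 8.2.2, and in both places in 9.4.4, change the trigger from above 12 to 12 or above.
2. Keep discontinuation at 12 or above in 7.1 and add a cross-reference there to the 8.2.2 assessment. Raising 7.1 to above 12 would also remove the mismatch, but by weakening the stop.
3. Reword 2.3.1 to follow the order already in 7.1 and 8.2.1. Clinicians decide whether an acute assessment is needed; if it shows significantly increased risk, stimulation is discontinued; the participant is invited to the 2-week follow-up unless the clinician ends participation or the participant is hospitalized. For suicidality the assessment must stay ahead of the stop.
4. Have 8.2.2 say that stimulation is discontinued and that the 7.1 follow-up invitation applies unless the clinician ends participation.

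The cost is a short wording amendment to four sections, with the IRB review that any amendment needs. Section 8.2.1 is unchanged. No visit or instrument is added; the only new work is a clinician's assessment when someone scores exactly 12.

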8.2 SAFETY AND OTHER ASSESSMENTS

8.2.1 SUICIDAL IDEATIONS AND SUICIDAL BEHAVIOR

Only subjects with a HDRS-17 suicidality item score of <3 and low suicide risk based on the C-SSRS are enrolled in this study. Furthermore, suicidal thoughts and behaviors will be assessed using a brief daily suicide survey (IRB# 14-0600) consisting of three questions. Participants will be asked if they had any thoughts of hurting themselves in the last 24 hours (suicidal ideation, SI) and whether they have hurt themselves in the past 24 hours (suicidal behavior, SB). They will also be asked to rate the severity of their depression on a scale of 1 to 10. Participants receive a link to answer the daily suicide survey on RedCap. To maximize participant's safety the daily suicide survey is send during the follow-up period as well. Responses will be monitored by study personnel daily and the last survey will be administered at the day of follow-up visit. In addition, the C-SSRS [13] will be administered by trained research personnel at screening, D1, D5 and the follow-up session to thoroughly assess suicide risk.

If a participant report experiencing either SI or SB on either tool, research personnel will collect more information from the participant to deliver to either [name] or [name]. Clinical personnel will decide if an acute assessment is required. Acute assessment may include facilitating contact of the subject with their psychiatrist or primary care physician to establish a plan for safety, continued care, and follow-up. If the participant does not have an established provider, [name] or [name] will assist in establishing a care plan. If at any point during the assessment, the participant is deemed an imminent risk of harm to self or others, study personnel will enlist the aid of campus security to ensure that the participant is safely escorted to the Emergency Department for further care. [name] and/or Dr.

[name] will decide if participation should be stopped after the acute assessment. If the participant is hospitalized, their participation will end.

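### The 72-hour limit and phone call for an unanswered daily suicide survey apply only to stopping stimulation, so the protocol requires no contact when a participant stops answering between Day 6 and the follow-up visit

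*Combined protocol and SAP*

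**What the plan says.** Section 7.1 opens its list with "The study intervention (i.e., the 5 consecutive days of stimulation) will be discontinued for the following reasons". One item in the list is a subject's failure to "complete the online suicidality questions within 72 hours of receiving the survey email and a personal phone contact does not explain the omission". The same section says that stopping stimulation does not end study participation.

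Section 8.2.1 states that "the daily suicide survey is send during the follow-up period as well", and gives participant safety as the reason. It continues: "Responses will be monitored by study personnel daily and the last survey will be administered at the day of follow-up visit". On content it says "Participants will be asked if they had any thoughts of hurting themselves in the last 24 hours", with a matching question on self-harm. On action it says "If a participant report experiencing either SI or SB on either tool, research personnel will collect more information from the participant", who then pass it to the study clinicians. Section 9.4.4 is parallel: where a participant's "responses on either tool indicate SI or SB, the subject will be contacted".

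The C-SSRS "will be administered by trained research personnel at screening, D1, D5 and the follow-up session". The schedule of activities (1.3) also places the HDRS-17 at D5 and follow-up, and sets the follow-up visit at Day 22 +/-3 days. Section 7.3 directs email and phone efforts at participants lost to follow-up, defined as missing the visit and being unreachable. It also mentions reminders of session dates.

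**The concern.** The protocol treats 72 hours of unexplained silence on the suicide survey as serious enough to withhold stimulation. That rule operates in the week when staff already see the participant daily. After Day 5 the in-person visits stop. From then until the follow-up C-SSRS and HDRS-17, the survey is the only scheduled suicide monitoring, and over that stretch no step is written for a survey that is not returned.

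Every action in 8.2.1 and 9.4.4 begins with a positive answer, which a silent participant does not give. Because the survey looks back only 24 hours, a later answer does not cover the missed days. What is at stake is how soon someone speaks to a depressed participant who has stopped responding.

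**Working it through.** **Inputs.** 72-hour limit and call (7.1); stimulation on D1 to D5 (1.1, 1.3); one missed session may be made up at the end of the week (5.5); surveys counted from D1 and sent to the day of the visit (1.3, 8.2.1); visit day V = 22, window 19 to 25 (1.3). The time of day at which the survey is sent is not stated. The plan gives no figure of its own to reproduce.

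**Which surveys can the 7.1 rule act on?** A survey sent on day d reaches its limit on day d + 3. It can stop a session only if the limit falls no later than the last session.

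D1 → Day 4, D2 → Day 5, D3 → Day 6, D4 → Day 7, D5 → Day 8.

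| Last session | Sent before the session hour | Sent after the session hour |
|---|---|---|
| Day 5 (planned) | D1, D2 | D1 |
| Day 6 (one make-up) | D1 to D3 | D1, D2 |
| Day 8 (make-up after a weekend; assumption) | D1 to D5 | D1 to D4 |

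Section 2.3.1 has daily evaluation start after enrolment. If surveys go out before D1, those earlier surveys are covered as well. A survey from Day 6 reaches its limit on Day 9 at the earliest, so none from Day 6 onward is covered in any row.

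**How many surveys lie outside the rule from Day 6?** Sent from Day 6 to V inclusive: V − 5. For V = 19, 22, 25 this is 14 of 19, 17 of 22 and 20 of 25.

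**How many of these would pass 72 hours before the visit?** This needs d + 3 < V, so d runs from 6 to V − 4, which is V − 9 surveys: 10, 13, 16.

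**How much earlier would a call come?** For silence from day s, the call is due on day s + 3 and the gain over waiting for the visit is max(0, V − s − 3).

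- s = 6: 10, 13, 16 days for V = 19, 22, 25. This is the maximum.
- V = 22: s = 12 gives 7 days, s = 18 gives 1, s = 19 or later gives 0.

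**Alternative reading of the visit date.** If two weeks is counted from Day 5, V = 19 with window 16 to 22. Surveys sent from Day 6: 11, 14, 17. Passing 72 hours before the visit: 7, 10, 13. Maximum gain: 7, 10, 13 days.

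**Does another section require contact for silence after Day 5?**

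- 8.2.1 and 9.4.4: triggered by reported ideation or behaviour.
- 8.2.1, daily monitoring: staff could see a gap, but no action on one is stated.
- 7.3: triggered by a missed visit. The reminders have no stated timing and are not safety checks.
- 2.3.1 (referral if risk rises) and 10.1.6 (investigator review of changes in suicidality ratings): both need a detected change.
- 10.1.7.1: the investigators can view missing-data reports by subject; no contact follows from that.
- 10.1.8: refers to SOPs without describing a non-response step.

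**The case against.** The strongest reply is that this is a matter of where a sentence sits. Staff review responses daily, the investigators can see missing data by subject, follow-up surveys exist expressly for safety, and 7.1 already treats a phone call as the natural response to an overdue survey. Staff may well call anyway. The SOPs, or the survey's own IRB file (8.2.1 cites the survey under a separate number), could hold a non-response procedure that is not visible here. All of that stands, and it limits the claim to what the published protocol requires. It does not supply the requirement.

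Entrants are screened to low risk and have a C-SSRS at D5. The follow-up C-SSRS and adverse event inquiry may recover ideation later. That also stands, and it is why the harm is delay and not necessarily lost information.

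A reader might go further in three ways that the documents do not support.

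- That the rule covers the D1 and D2 surveys and no others. That count holds for the planned schedule with surveys counted from D1 and emailed before the session. It changes with send time, a make-up session or an earlier survey start.
- That the previous trial shows excess risk in this window. Section 2.3.1 reports increased suicidal thoughts in 4 sham subjects, one with intent, and none among those who received tACS. Timing is not stated and nothing ties these events to survey silence, so they are context only.
- That the day counts measure expected harm. They measure opportunity, and the largest gain needs complete silence from Day 6.

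**Conclusion.** The point holds for the protocol as published: non-response to the suicide survey from Day 6 to the follow-up visit triggers no required contact, deadline or referral. A safety step that the plan itself adopts lapses for 17 of 22 surveys on a Day 22 visit (14 of 19 to 20 of 25 over the window). Extending it would bring contact forward by at most 13 days (10 to 16), falling to 0 for silence that starts on Day 19 or later.

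This rests on surveys counted from D1, the Day 22 +/-3 visit in the schedule, and no further procedure in documents not seen. The documents give no non-response rate, so neither the number of participants affected nor the number of calls can be estimated. The endpoints and the analysis are not touched. It is a cheap improvement in participant safety that should be made.

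**What to change.** Amend 8.2.1 so that the existing personal phone contact applies, at 72 hours at the latest, to any overdue daily survey through the follow-up visit, whether or not stimulation is still under way. Make one call per continuous run of missed surveys. If contact fails or does not explain the omission, refer to the study clinicians. At the call, ask about the whole interval since the last completed survey. Leave the survey itself unchanged, since it is cited under its own IRB number, and leave the 7.1 stopping rule as it is. If an SOP already requires the call, cite it in 8.2.1.

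The cost is an amendment with IRB approval before use, plus calls by staff who already monitor responses daily. The number of calls is unknown but bounded. With all visits on Day 22, at most 13 × 20 = 260 surveys from Day 6 could pass 72 hours before the visit. Calling once per run keeps the number of calls below that; a participant silent throughout generates one.
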